11.1.4.4 Evaluation of Best Overall Response

The best overall response is the best response recorded from the start of the treatment until disease progression/recurrence (taking as reference for progressive disease the smallest measurements recorded since the treatment started). The patient's best response assignment will depend on the achievement of both measurement and confirmation criteria.

For Participants with Measurable Disease (*i.e.*, Target Disease)

Target Lesions	Non-Target Lesions	New Lesions	Overall Response	Best Overall Response when Confirmation is Required*
CR	CR	No	CR	≥4 wks Confirmation**
CR	Non-CR/Non-PD	No	PR	≥4 wks Confirmation**
CR	Not evaluated	No	PR	
PR	Non-CR/Non-PD/not evaluated	No	PR	
SD	Non-CR/Non-PD/not	No	SD	Documented at least once ≥4 wks from baseline**

Version Date: June 20, 2018

	evaluated			
PD	Any	Yes or No	PD	no prior SD, PR or CR
Any	PD***	Yes or No	PD	
Any	Any	Yes	PD	

* See RECIST 1.1 manuscript for further details on what is evidence of a new lesion.
 
** Only for non-randomized trials with response as primary endpoint.
 
*** In exceptional circumstances, unequivocal progression in non-target lesions may be accepted as disease progression.
 
Note: Participants with a global deterioration of health status requiring discontinuation of treatment without objective evidence of disease progression at that time should be reported as “symptomatic deterioration.” Every effort should be made to document the objective progression even after discontinuation of treatment.
				

For Participants with Non-Measurable Disease (*i.e.*, Non-Target Disease)

Non-Target Lesions	New Lesions	Overall Response
CR	No	CR
Non-CR/non-PD	No	Non-CR/non-PD*
Not all evaluated	No	not evaluated
Unequivocal PD	Yes or No	PD
Any	Yes	PD

* ‘Non-CR/non-PD’ is preferred over ‘stable disease’ for non-target disease since SD is increasingly used as an endpoint for assessment of efficacy in some trials so to assign this category when no lesions can be measured is not advised
		

11.1.5 Duration of Response

Duration of overall response: The duration of overall response is measured from the time measurement criteria are met for CR or PR (whichever is first recorded) until the first date that recurrent or progressive disease is objectively documented (taking as reference for progressive disease the smallest measurements recorded since the treatment started, or death due to any cause. Participants without events reported are censored at the last disease evaluation).

Duration of overall complete response: The duration of overall CR is measured from the time measurement criteria are first met for CR until the first date that progressive disease is objectively documented, or death due to any cause. Participants without events reported are censored at the last disease evaluation.

Protocol *A pilot study to evaluate PBR PET as an indicator of inflammation in brain tumor patients treated with chemoradiation or immunotherapy.*

Version Date: June 20, 2018

Duration of stable disease: Stable disease is measured from the start of the treatment until the criteria for progression are met, taking as reference the smallest measurements recorded since the treatment started, including the baseline measurements.

11.1.6 Progression-Free Survival

Overall Survival: Overall Survival (OS) is defined as the time from randomization (or registration) to death due to any cause, or censored at date last known alive.

Progression-Free Survival: Progression-Free Survival (PFS) is defined as the time from randomization (or registration) to the earlier of progression or death due to any cause. Participants alive without disease progression are censored at date of last disease evaluation.

Time to Progression: Time to Progression (TTP) is defined as the time from randomization (or registration) to progression, or censored at date of last disease evaluation for those without progression reported.

11.1.7 Response Review

NA

11.2 **Antitumor Effect – Hematologic Tumors**

NA

11.3 **Other Response Parameters**

NA

DATA REPORTING / REGULATORY REQUIREMENTS

Adverse event lists, guidelines, and instructions for AE reporting can be found in Section 7.0 (Adverse Events: List and Reporting Requirements).

12.1 **Data Reporting**

12.1.1 Method

The QACT will collect, manage, and perform quality checks on the data for this study.

12.1.2 Responsibility for Data Submission

Protocol *A pilot study to evaluate PBR PET as an indicator of inflammation in brain tumor patients treated with chemoradiation or immunotherapy.*

Version Date: June 20, 2018

Investigative sites within DF/HCC or DF/PCC are responsible for submitting data and/or data forms to the QACT according to the schedule set by the QACT.

12.2 Data Safety Monitoring

The DF/HCC Data and Safety Monitoring Committee (DSMC) will review and monitor toxicity and accrual data from this study. The committee is composed of clinical specialists with experience in oncology and who have no direct relationship with the study. Information that raises any questions about participant safety will be addressed with the Overall PI and study team.

The DSMC will review each protocol up to four times a year or more often if required to review toxicity and accrual data. Information to be provided to the committee may include: up-to-date participant accrual; current dose level information; DLT information; all grade 2 or higher unexpected adverse events that have been reported; summary of all deaths occurring within 30 days of intervention for Phase I or II protocols; for gene therapy protocols, summary of all deaths while being treated and during active follow-up; any response information; audit results, and a summary provided by the study team. Other information (e.g. scans, laboratory values) will be provided upon request.

12.3 Multicenter Guidelines

NA

12.4 Collaborative Agreements Language

NA

STATISTICAL CONSIDERATIONS

13.1 Study Design/Endpoints

This is a pilot study to test the potential utility of PBR28 PET in measuring treatment related inflammation . We will measure if increased uptake of PBR28 in the tumor during treatment is associated with longer time to progression (i.e. suggesting that the response to therapy is inflammatory rather than tumor growth).

13.2 Sample Size, Accrual Rate and Study Duration

Version Date: June 20, 2018

Total sample size is anticipated to be 40 patients: 15 patients in cohort A (metastatic brain tumor patients) and 15 in cohort C (GBM patients suspected of having pseudoprogression) and 10 in cohort B (GBM patients treated with immunotherapy).

Several factors influence the sample size for this study. This is a non-therapeutic study in a patient population which typically chooses to enroll in therapeutic trials if they are going to participate in a clinical trial at all so this trial will be less appealing to patients. In addition, since PBR PET remains investigational it is a very expensive test so budgetary constraints limit accrual.

In order to assess if PBR PET helps to assess tumor inflammation, we will quantitate PBR uptake in the tumor and correlate that with tumor progression as determined by the treating physician or tissue histology if obtained. The hypothesis is that if tumor PBR retention is high, this would be consistent with a strong response to immunotherapy and should be associated with prolonged progression free survival. If PBR retention is low, indicating an immunosuppressive, active tumor microenvironment, PFS should be short. We selected 9 months because by this time, we should know who has true progression since treatment related inflammation has peaked by this time.

The aim of this study is to demonstrate higher levels of PBR uptake in the non-progression group. Therefore the sample size calculation is based on two group means comparison and the test used is a one-sided two-sample equal variance t-test (with mean and SD estimates as cited below). Since there is no a priori indication for the breakdown between progression and non-progression, we assumed equal group sizes.

With 15 patients in cohort A (metastatic brain tumor patients) and 15 in cohort C (GBM patients suspected of having pseudoprogression), the study will have at least 80% power to detect a 60% difference in PBR uptake between those progression free at 9 months and those not progression free at 9 months using a one-side hypothesis test with a 0.1 significance level. By 9 months, we should know who has true progression and who has pseudoprogression. Patients who die before nine months will be considered true tumor progression. Given this conservative approach we will have the power to detect a smaller difference in PBR uptake.

For the patients who have baseline and mid treatment PET (cohort A), we will use the change in PBR uptake. There is limited data on PBR28 in brain tumors so this calculation assumes a baseline of 125 ml/cm³ and equal variance of 100 ml/cm³ (based on literature reported rates from healthy brain).⁹ PFS at 9 months was selected as most patients would have progressed at 9 months. All patients will also be followed for 3 years after study completion for progression and survival. Time to event analysis will be used to incorporate other potential prognostic factors such as age and functional status.

Protocol *A pilot study to evaluate PBR PET as an indicator of inflammation in brain tumor patients treated with chemoradiation or immunotherapy.*

Version Date: June 20, 2018

Given the small number of patients anticipated to accrue to cohort B (GBM patients treated with immunotherapy), these patients will be analyzed with descriptive statistics alone. This accrual is anticipated to be low because of the small number of GBM patients currently treated with immunotherapy. We anticipate enrolling a maximum of 10 patients in this cohort.

Accrual Targets					
Ethnic Category	Sex/Gender				
	Females		Males		Total
Hispanic or Latino	2	+	2	=	4
Not Hispanic or Latino	3	+	8	=	11
Ethnic Category: Total of all subjects	5	+	10	=	15
Racial Category					
American Indian or Alaskan Native	0	+	0	=	0
Asian	0	+	1	=	1
Black or African American	0	+	1	=	1
Native Hawaiian or other Pacific Islander	0	+	0	=	0
White	5	+	8	=	13
Racial Category: Total of all subjects	5	+	10	=	15

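### Section 13.2 claims at least 80% power for a 60% difference, but its own inputs give 77% with cohorts A and C pooled in equal groups, and about 55% within one cohort if the SD is 100

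*Combined protocol and SAP*

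**What the plan says.** All the design inputs are in section 13.2 (Sample Size, Accrual Rate and Study Duration):

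- **Test:** "the test used is a one-sided two-sample equal variance t-test (with mean and SD estimates as cited below"), with the progressed and progression-free groups assumed equal in size because nothing was known in advance about the split.
- **Error rate:** "using a one-side hypothesis test with a 0.1 significance level".
- **Numbers and claim:** "With 15 patients in cohort A (metastatic brain tumor patients) and 15 in cohort C (GBM patients suspected of having pseudoprogression"), the study is said to have "at least 80% power to detect a 60% difference in PBR uptake between those progression free at 9 months" and those not.
- **Mean and spread:** "this calculation assumes a baseline of 125 ml/cm³ and equal variance of 100 ml/cm³", taken from published values for healthy brain.
- **Deaths:** a death before nine months counts as true progression. The next sentence reads "Given this conservative approach we will have the power to detect a smaller difference in PBR uptake".
- **Measure:** cohort A is analysed on the change in uptake between two scans. Under section 5.1 and the Study Calendar, cohort C has one scan.
- **Expected split:** the same section justifies the 9-month time point by saying that most patients would have progressed by then.
- **Cohort B:** descriptive statistics only, so it is outside the power statement.

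Section 13.5 (Analysis of Primary Endpoints) only refers back to this text. Nowhere does the plan say whether A and C are tested together or separately.

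**The concern.** The power sentence is the plan's only formal justification of the sample size, and every input needed to check it is given. The claim is a lower bound, so it fails if those inputs give less than 80%.

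Three features of the text make the figure doubtful. The spread is called an SD in one place and a variance in another. The claim does not say whether it covers 30 patients or each cohort of 15. The equal split sits beside a statement that most patients will have progressed.

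Section 2.4 (Rationale) says the tracer will be examined further in phase II vaccination studies if it shows potential utility here. A negative result judged against 80% power would look stronger evidence against the tracer than the design can supply.

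**Working it through.** **Inputs.** Difference Δ = 0.60 × 125 = 75 ml/cm³. SD σ = 100 ml/cm³. One-sided α = 0.10. Pooled groups 15 v 15; a single cohort of 15 splits as 7 v 8. No dropout is stated, so none is taken.

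**Why 100 is read as an SD.** The units are not squared, and the text naming the test refers to SD estimates. A literal variance of 100 means SD = 10 and a standardised difference of 75/10 = 7.5. Power then exceeds 99.99% with only 2 patients per group, so that reading cannot have led to 30 patients.

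**Formula.** With n₁ and n₂ patients, the noncentrality is λ = Δ / (σ√(1/n₁ + 1/n₂)) and df = n₁ + n₂ − 2. Power is the probability that a noncentral t(df, λ) exceeds the 90th percentile of the central t.

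**Attempt to reproduce the 80%.** At 15 v 15, λ = 0.75 / √(2/15) = 2.054, df = 28, critical value 1.313, power **77.1%**. A simulation of 200,000 trials gave 77.2%. The normal approximation gives Φ(2.054 − 1.282) = 78.0%. Neither reaches 80%.

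| Groups | λ | df | Power |
|---|---|---|---|
| 15 v 15 (A and C pooled) | 2.054 | 28 | 77.1% |
| 16 v 16 | 2.121 | 30 | 79.1% |
| 17 v 17 | 2.187 | 32 | 81.0% |
| 10 v 20 (pooled, illustrative) | 1.936 | 28 | 73.4% |
| 6 v 24 (pooled, illustrative) | 1.643 | 28 | 63.2% |
| 7 v 8 (one cohort) | 1.449 | 13 | 54.8% |

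The unequal splits are illustrative because the plan gives no percentage for progression at 9 months.

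**Difference detectable with 80% power (σ = 100).** At 15 v 15: 78.7 ml/cm³, and 78.7/125 = 63%. At 7 v 8: 113.6 ml/cm³, and 113.6/125 = 91%. Keeping the 60% difference at 15 v 15, the SD would have to be about 95.3 or less.

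**Cohort A on change.** The plan gives no SD for the change. If each scan has SD 100 and the within-patient correlation is ρ, the SD of change is 100√(2(1 − ρ)). For a 75-unit difference at 7 v 8:

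| ρ | SD of change | Power |
|---|---|---|
| 0 | 141 | 39% |
| 0.5 | 100 | 55% |
| 0.75 | 71 | 76% |
| 0.8 | 63 | 83% |

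The 55% therefore holds for cohort A only if the SD of change is itself 100.

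**Deaths counted as progression.** The calculation already places all 30 patients in two equal groups. The rule adds no patient to those 30 and does not lower the SD, so it gives no gain over 77.1%.

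**The case against.** The strongest reply is about size. The power sentence reads most naturally as 30 patients in two equal groups. On that reading the shortfall is 2.9 points (2.0 by the normal approximation), or a detectable difference of 63% instead of 60%. This is a pilot whose numbers, the plan says openly, are limited by patient interest and budget. That stands: the pooled gap alone is small.

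A reader might go further and infer that the plan promises 80% within each cohort and delivers 55%. The documents do not support this. The plan makes no per-cohort claim, and the 55% carries over to cohort A only under an SD of change that it does not state; with a high enough within-patient correlation, power in cohort A could pass 80%. Nor do the different measures in A and C force separate tests, since a stratified or standardised analysis is possible. What stands is that the plan chooses none of these.

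A reader might also infer that counting deaths as progression moves patients between groups and worsens the balance. Section 11.1.6 already defines PFS by progression or death from any cause, so under that definition nobody moves. Compared with leaving early deaths out, the rule helps: losing five patients from one group, for example, gives 15 v 10 and 69.9%. But the calculation already uses 15 v 15, so the rule cannot support a claim of power beyond it.

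Finally, the accrual table in section 13.2 (row "Ethnic Category: Total of all subjects") adds to 15, whereas "Total sample size is anticipated to be 40 patients". This is a clerical mismatch with no bearing on power.

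**Conclusion.** The concern holds in a limited form. With the named test, SD 100 and cohorts A and C only, neither the pooled nor the single-cohort reading reaches 80%.

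- **Pooled, equal groups:** 77%, a small shortfall.
- **Pooled, unequal groups:** lower, for example 73% at 10 v 20 and 63% at 6 v 24. The plan's own expectation that most patients will have progressed makes imbalance likely.
- **Single cohort:** about 55%, conditional on an SD of 100 for the measure used.

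These figures rest on reading 100 as an SD, on healthy-brain values applying to tumour, and on no dropout. The pooled figures also treat cohort A's change and cohort C's single-scan uptake as having the same SD and the same target difference. The material weakness is less the 3 points than the undefined analysis: whether the cohorts are combined moves the power between 77% and about 55% when the SD is 100. The sentence is wrong as written and cheap to correct.

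**What to change.** All changes are to section 13.2.

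1. Check the value of 100 ml/cm³ against the cited source. Once the sponsor has confirmed it, replace the word variance with SD.
2. State whether A and C are tested together or separately and, if together, how change in A and a single scan in C are combined.
3. Replace the power sentence with, for example: *77% power for a 60% difference (80% for 63%) if A and C are combined in equal groups, falling to 73% at 10 v 20 and 63% at 6 v 24; about 55% (80% for 91%) within a single cohort, assuming an SD of 100 for the measure used, including change in cohort A.*
4. Delete the sentence claiming power for a smaller difference. The rule on early deaths can stay.

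The cost is wording and a less favourable stated power. No patients, scans or procedures are added. The accrual table total can be reconciled with the planned 40 in the same amendment; the sponsor must supply the sex, ethnicity and race breakdown.

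### Section 13.2 says that counting all deaths before 9 months as progression allows a smaller uptake difference to be detected; against the plan's own calculation the rule leaves the detectable difference unchanged or makes it larger

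*Combined protocol and SAP*

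**What the plan says.** Section 13.2 sizes the study on a comparison of mean PBR uptake in two groups defined by status at 9 months. It states that "the study will have at least 80% power to detect a 60% difference in PBR uptake", "using a one-side hypothesis test with a 0.1 significance level", with 15 patients in each of cohorts A and C and with equal groups assumed. Progression is to be judged clinically or on tissue; the plan will "correlate that with tumor progression as determined by the treating physician or tissue histology if obtained".

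The same section then adds a rule for deaths: "Patients who die before nine months will be considered true tumor progression". The next sentence draws a consequence: "Given this conservative approach we will have the power to detect a smaller difference in PBR uptake". The plan gives no calculation for this, no expected number or cause of deaths, and no other way of handling deaths with which the rule is being compared. The only figure in the paragraph to which the word smaller can refer is the 60% difference.

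Two other statements bear on the point. Section 11.1.6 defines progression-free survival so that death from any cause is an event. Section 13.2 expects most patients to have progressed by 9 months.

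**The concern.** A rule for labelling patients can improve on a power calculation only if the calculation left something out, such as patients not counted or labels assumed to be imperfect. This calculation already uses all 30 patients, in correctly labelled groups of the most favourable sizes. A rule that may place some patients with non-progressor uptake in the progression group pulls the two means together. That is conservative in the usual sense, and it costs power.

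At stake is how the result will be read. Anyone relying on the sentence could take a null result as evidence against differences below 60%, a sensitivity that the design does not have. The study is a pilot and no decision rule depends on the sentence, but its results are meant to inform later phase II work.

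**Working it through.** **Inputs, all from section 13.2**
- Contrast: to "detect a 60% difference in PBR uptake between those progression free at 9 months and those not progression free at 9 months".
- Mean and spread: "this calculation assumes a baseline of 125 ml/cm³ and equal variance of 100 ml/cm³". The difference is therefore 0.60 × 125 = 75 ml/cm³.
- Test: "the test used is a one-sided two-sample equal variance t-test (with mean and SD estimates as cited below". The figure of 100 is called a variance, but it carries the units of the mean and the test description speaks of SD estimates, so it is read here as the SD.
- One-sided alpha 0.10.
- N = 15 + 15 = 30. Cohorts A and C are taken as pooled and split 15 v 15 by progression. Cohort B is descriptive only.

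**Step 1: the plan's own figure**
- Standard error = 100 × √(1/15 + 1/15) = 36.5. Noncentrality = 75 / 36.5 = 2.05.
- Normal approximation: Φ(2.05 − 1.28) = 78.0%.
- Noncentral t with 28 df: 77.1%.
- Detectable difference at 80% power: 36.5 × (1.28 + 0.84) = 77.5 ml/cm³ by the normal approximation (62% of 125); 78.7 by the t-test (63%).

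The stated 80% is reproduced only roughly. The named t-test would need 17 per group. There is no reserve from which a smaller detectable difference could come.

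**Step 2: group sizes alone (labels correct, N = 30, SD 100)**

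The detectable difference scales with √(1/n₁ + 1/n₂), which is smallest at equal sizes.

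| Progressed / not | Detectable difference at 80% power (ml/cm³) |
|---|---|
| 15 / 15 | 78.7 |
| 18 / 12 | 80.3 |
| 20 / 10 | 83.5 |
| 22 / 8 | 89.0 |

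As the plan expects most patients to have progressed, adding deaths to that group moves further from balance.

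**Step 3: deaths that are tumor progression**

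The calculation already counts these patients as progressed, so the figure stays at 78.7. The same holds if the PFS definition in 11.1.6 governs 9-month status, because death is then already an event.

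**Step 4: deaths without tumor progression**

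Suppose k patients with non-progressor uptake die early and are labelled as progression. The values of k are assumed, since the documents give none. Two models were simulated with the pooled-variance one-sided t-test:
- Model 1: labelled groups stay at 15 / 15, with k of the 15 misassigned. The expected observed difference is 75 × (15 − k)/15: 70, 65 and 60 for k = 1, 2, 3. The variance in the progression group also grows; for k = 3 it is 100² + 75² × 0.2 × 0.8 = 10,900.
- Model 2: the true split is 15 / 15 and k patients move across. The expected observed difference is 75 × 15/(15 + k): 70.3, 66.2 and 62.5.

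| k | Power at 75, model 1 | Power at 75, model 2 | Detectable, model 1 (ml/cm³) | Detectable, model 2 (ml/cm³) |
|---|---|---|---|---|
| 0 | 77% | 77% | 79 | 79 |
| 1 | 72% | 72.5% | 85 | 84.9 |
| 2 | 67% | 67.9% | 92 | 91.0 |
| 3 | 62% | 63.4% | 101 | 98.8 |

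As a share of the baseline of 125, the detectable difference goes from 63% to 68% (k = 1), 73-74% (k = 2) and 79-81% (k = 3).

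**Step 5: when the rule would help**
- If 4 tumor deaths would otherwise be excluded, the comparison is 11 v 15: power 71.7%, detectable difference 85.8. The rule restores 77.1% and 78.7.
- If 2 tumor deaths would otherwise be counted as progression-free, power is 67.9% without the rule and about 77% with it.
- With 4 deaths of mixed cause, the rule and exclusion are about equal if 3 are tumor deaths (72.8% v 72.3%). The rule is worse if only 2 are (68.0% v 72.5%).

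In none of these cases does the rule take the detectable difference below 78.7.

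**The case against.** The strongest reply is that the effect of the rule depends on what would otherwise happen to these patients. In brain tumor patients, many early deaths may well be tumor deaths without a documented progression. Excluding them loses patients and calling them progression-free mislabels them, so the rule is better than either (step 5). This stands. A reader might infer that the rule can only do harm, or that it makes this trial less sensitive as a matter of fact. The documents support neither, because they give no number or cause of deaths and no alternative handling. But the plan does not propose exclusion or a progression-free label either, and even against those the rule only brings sensitivity back towards the planned figure.

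A second reply is that section 11.1.6 already makes death from any cause a PFS event, so the rule merely restates the endpoint and misassigns nobody. A reader might otherwise see a contradiction between physician-determined progression and the death rule. With 11.1.6 in view that is too strong, although section 11 is offered only as reference for the treating physician and 13.2 does speak of true tumor progression. Either way the reply does not rescue the sentence: a rule that restates the endpoint adds no power.

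Third, the dilution figures rest on assumed counts and a chosen model. This also stands. They show direction and rough size, and are not forecasts.

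**Conclusion.** The sentence has no basis in the plan. Against the plan's own calculation, the death rule leaves the detectable difference at about 79 ml/cm³ (63% of baseline) or raises it, to about 85, 91-92 or 99-101 ml/cm³ with an assumed 1, 2 or 3 deaths without tumor progression. Power at 75 falls from 77% to about 72%, 67-68% and 62-63%.

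This rests on three assumptions: 100 is the SD, cohorts A and C are pooled, and no patients are lost. Pooling is not stated explicitly, and cohort A uses change in uptake while cohort C has a single scan. A single cohort at 8 v 7 would have 54.8% power at 75, so there would be even less room. If 100 were literally the variance (SD 10), the detectable difference would be about 7.9 ml/cm³. That would not come from the death rule, which still could not improve on correctly labelled equal groups.

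The defect is an unsupported statement about sensitivity. The rule itself may be reasonable, and nothing here argues for dropping it.

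**What to change.** - Delete the sentence "Given this conservative approach we will have the power to detect a smaller difference in PBR uptake". In its place, say that deaths without tumor progression, if counted as progression, may dilute the difference in uptake.
- If a detectable difference is quoted, restate the claim of 80% power for 60% in the same paragraph so that the two agree. Adding 63% at 80% power beside the present claim would create a contradiction.
- State whether 9-month status follows the PFS definition in 11.1.6.
- Add one sensitivity comparison that leaves out deaths before 9 months without documented tumor progression. The 3-monthly follow-up in the study calendar records response and survival, which is enough for this definition. It does not list cause of death, so a comparison based on cause would need that item added.

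The cost is a wording change in 13.2, one extra analysis and a less favourable stated sensitivity. The comparison should be read as a check only, because leaving out deaths that were in fact due to tumor also loses power (step 5).

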5. IMAGING PLAN

5.1 Treatment Regimen

This study does not add any additional treatment to enrolled patients. All treatment decisions will be at the discretion of the treating physician. There will be no change in the diagnosis or management of the patient based on any procedures or tests carried out as a part of this study.

There are no expected toxicities and potential risks for PBR. All scans will be performed at the Martinos Center for Biomedical Imaging in Charlestown on the combined MR PET scanner.

For GBM patients with suspected pseudoprogression, MR-PET will be performed at the time of suspected pseudoprogression.

For GBM patients treated with immunotherapy, MR-PET will be performed prior to start of the immunotherapy and then 2 cycles later.

For metastatic cancer patients treated with immunotherapy, MR-PET will be performed prior to start of the immunotherapy and then 3 cycles later.

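### One power figure covers cohorts A and C together, but A supplies a change in uptake and C a single level, and the plan does not say how the two are combined

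*Combined protocol and SAP*

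**What the plan says.** Section 13.2 names one comparison, patients progression-free at 9 months against those who are not, and one test: "the test used is a one-sided two-sample equal variance t-test (with mean and SD estimates as cited below". On the split between the two outcome groups it says "we assumed equal group sizes".

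The power sentence takes both cohorts together and opens "With 15 patients in cohort A (metastatic brain tumor patients) and 15 in cohort C". For that combined total it claims "at least 80% power to detect a 60% difference in PBR uptake". The error rate behind the claim is given as "using a one-side hypothesis test with a 0.1 significance level". The inputs are a baseline of 125 ml/cm³ and a spread of 100 ml/cm³, taken from healthy brain. The spread is called a variance at that point but an SD in the description of the test. Its unit is that of an SD, and it is read as one here.

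The same section then sets the variable for one cohort: "For the patients who have baseline and mid treatment PET (cohort A), we will use the change in PBR uptake". Cohort C cannot supply a change. Section 5.1 says "For GBM patients with suspected pseudoprogression, MR-PET will be performed at the time of suspected pseudoprogression", and the Study Calendar shows one PET for that cohort.

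Section 13.3 (stratification) is NA. Section 13.5 (primary analysis) only refers back to the text above it. Cohort B is descriptive and plays no part in this test.

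**The concern.** A change score centres on the average change. A single-scan value centres on the average level, which the plan puts near 125. If both go into one two-sample t-test, cohort membership shifts the measured value. If 9-month progression-free survival (PFS) also differs between cohorts, membership shifts the outcome group too. The test could then find a difference, or hide one, when uptake and progression are unrelated within either cohort. If PFS is the same in both, the offset between scales only adds variance and lowers power.

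The power calculation has a separate gap. It applies one absolute-scale mean and SD to all patients. No SD is given for a change, and a 60% difference has no stated meaning for one.

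**Working it through.** **Step 1. Reproduce the stated power.** Inputs from 13.2: difference 0.60 × 125 = 75; SD 100; one-sided alpha 0.10; equal groups. For group sizes n1 and n2, the noncentrality is 75 / (100 × √(1/n1 + 1/n2)), and power is the upper tail of the noncentral t beyond the 0.90 quantile of t.

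- A and C pooled, 15 v 15: noncentrality 2.054, critical value 1.313 (28 df), power **0.771** (0.780 by the normal approximation).
- One cohort alone, 7 v 8: noncentrality 1.449, critical value 1.350 (13 df), power **0.548**.

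Pooling is therefore the closest reading. Neither reading gives 80%, which needs 17 per group (exact power 0.810).

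**Step 2. Type I error of an unadjusted pooled test.** These are assumptions, because the documents give neither PFS by cohort nor a mean change: 15 patients per cohort; normal values with SD 100 in both; cohort C mean 125; no association between uptake and progression within either cohort; 200,000 simulated trials per scenario; nominal one-sided 0.10.

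| 9-month PFS, A / C | Pooled, A mean change 0 | Pooled, A mean change 50 | With cohort term, change 0 |
|---|---|---|---|
| 30% / 30% | 0.100 | 0.100 | 0.100 |
| 50% / 50% | 0.099 | 0.101 | 0.100 |
| 30% / 40% | 0.165 | 0.139 | 0.100 |
| 30% / 50% | 0.247 | 0.186 | 0.100 |
| 30% / 60% | 0.346 | 0.243 | 0.100 |
| 40% / 30% | 0.056 | 0.069 | 0.100 |
| 50% / 30% | 0.030 | 0.046 | 0.100 |
| 60% / 30% | 0.015 | 0.031 | 0.100 |

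If the two cohort means are equal (both 125), the pooled error stays at about 0.10 in every row. The distortion needs unequal means and unequal PFS together.

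**Step 3. Power for a true 75-unit difference within each cohort.** With PFS 50% in both and mean change 0: 0.65 pooled and 0.75 with a cohort term. With a cohort term, power is 0.73 at 40/60% and 0.69 at 30/70%. If the cohort means were equal, the pooled test would have 0.76 at 50/50%.

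**Step 4. The SD of a change.** If each scan has SD 100 and the within-patient correlation is rho, the SD of the change is 100 × √(2(1 − rho)).

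| rho | SD of change | Power, cohort A alone (7 v 8) | Power, 15 v 15, if this SD held for all |
|---|---|---|---|
| 0 | 141 | 0.39 | 0.56 |
| 0.5 | 100 | 0.55 | 0.77 |
| 0.75 | 71 | 0.76 | 0.94 |
| 0.9 | 45 | 0.97 | over 0.99 |

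The plan's 100 fits a change only if rho is 0.5, and no rho is given.

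**Step 5. Separate tests.** Two independent tests at 0.10 have a family-wise error of 1 − 0.90² = 0.19. For 80% power, 7 v 8 needs a difference of about 114, which is 114/125 = 91% of the assumed baseline.

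**The case against.** The strongest reply is that the plan never says the two sets of values enter one test. Section 1.2 lists immunotherapy and chemoradiation as separate primary objectives, section 2.4 treats differences by cancer type as a goal, and giving cohort A its own variable fits a cohort-by-cohort analysis. This stands: pooling is inferred. But on the separate reading the power is 0.55 per cohort, further from the stated figure, so the text needs correcting either way.

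A reader might infer that the test has the wrong error rate outright. The documents do not support that. The error is nominal when PFS or the cohort means are equal, and 13.2 says there is no prior indication of the split between outcome groups. It also expects most patients to have progressed by 9 months, which makes the milder rows (30/40% and 40/30%) easier to square with the plan than those with 50% or 60%.

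A reader might also infer that the power calculation itself mixes change and level. It does not. It uses one absolute-scale mean and SD throughout, and so fails to match cohort A's variable.

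A cohort term is not a complete cure. If the SD of change were 45 against 100 in cohort C, it would give a type I error of about 0.13 to 0.14 at 10/50% and 0.06 at 50/10%. The planned time-to-event analysis offers little relief: it names age and functional status as examples, not cohort, and it is not the powered test.

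Finally, this is a pilot and no care decision uses the scans. That bears on severity, but the plan still states a formal test, an alpha and a power.

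**Conclusion.** The point holds as an unspecified combination of two different measures, with consequences that depend on facts the documents do not give. On the closest reading, an unadjusted pooled test at nominal 0.10 could have a type I error of about 0.16 to 0.35 if PFS is lower in A, or about 0.015 to 0.06 if it is higher. These ranges assume SD 100 in both cohorts, a cohort C mean of 125 and a mean change of 0; a mean change of 50 narrows them. With equal 50% rates the cost is power, about 0.65 v 0.75. Neither the pooled nor the separate reading delivers the stated 80%.

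It would go too far to say that the plan prescribes unadjusted pooling, or that the two cohorts are known to differ in 9-month PFS. For a pilot this ranks below a must-fix, but it should be settled before uptake is compared with outcome, because a choice made afterwards would be data-driven.

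**What to change.** In 13.2 and 13.5, state that A and C are not pooled unadjusted. Make the primary test a cohort-stratified comparison: a linear model of uptake on 9-month status with a cohort term, or uptake standardised within cohort. Allow for unequal variances if the SD of change differs from the SD of a level. Say whether cohort A's change is absolute or percent, and what a 60% difference means for it.

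Restate the power as about 0.69 to 0.75 under SD 100 in both cohorts and the splits tried here (50/50% to 30/70%). Add a range for the SD of change using 100 × √(2(1 − rho)).

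If separate tests are preferred, state about 0.55 power for each under SD 100, and a family-wise error of about 0.19 at 0.10 per test.

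The cost is wording, one degree of freedom for the cohort term, and a less favourable stated power. No extra patients or scans are needed.
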